## 9.3.5 Baseline Descriptive Statistics

In this longitudinal study, each participant will participate in both an exercise phase. Therefore, there will be no comparison between groups.

### 9.3.6 Exploratory Analyses

The exploratory objective to identify baseline factors (e.g., age, MNSI, general activity) predictive of improvement, represented as the baseline to follow-up change in each outcome, will be addressed using linear regression and bivariate correlations. This analysis will be stratified by intervention and then conducted using data from both phases combined. In each case, the assessment of compliance will be included as a weighting factor

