# 9.2 Statistical Hypotheses

**Hypothesis 1a:** Exercise will improve peripheral nerve integrity (DTI fractional anisotropy will increase, and the apparent diffusion coefficient will decrease).

Hypothesis 1b: Exercise will decrease plasma ROS levels.

Hypothesis 1c: Exercise will improve DPN symptoms, assessed with the MNSI.

**Hypothesis 2a:** Exercise will increase leg mitochondrial function, as defined by an increase in oxidative capacity (measured using P-MRI).

**Hypothesis 2b:** Exercise will improve leg MV function, as defined by an increase in peak MV response (measured using BOLD-MRI).

**Hypothesis 2c:** Exercise will decrease intramuscular fat and increase levels of fat-free muscle (measured using IDEAL-MRI).

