# 9.3.2 Analysis of the Primary Efficacy Endpoint(s)

A matched-pairs Wilcoxon signed rank test will be applied to the within-subject change in each outcome among subjects demonstrating full compliance with the exercise program. Additionally, weighted analysis of covariance (ANCOVA) will be used to test the change in each outcome adjusting for the measured level of compliance using data from all subjects. The values of each outcome at

CONFIDENTIAL

baseline and follow-up for all subjects will be the dependent variable and the ANCOVA model will include time (baseline versus follow-up) as the within-subject factor of interest covariates, the measure of compliance as numeric covariate and an anonymized subject ID as a classification factor so that the comparison of times will be based on their within-subject difference. The secondary objective is to assess the extent to which exercise induced improvements in DTI outcomes are can be at least partially explained by reduction in ROS will be addressed using linear regression, The baseline to follow-up change in each outcome will be the dependent variable and the model will include the measure of compliance as a numeric factor and the within-subject change in ROS as the numeric factor of interest. A second regression will be conducted with baseline factors (e.g., age, MNSI, general activity) added to the model in order to identify factors predictive of improvement in each outcome.

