## 9.4 Sample Size

Assessment of statistical power was based on tests conducted at the two-sided 5% significance level and the preliminary data in Table 3. Under the conservative assumption of a moderate within-subject correlation ( $\rho$ =0.5) between baseline and follow-up measures, the expected mean and SD of the within-subject change in the outcomes is given in Table 4. It is noted that statistical power will be higher if  $\rho$ >0.5 as observed in

Table 3. The mean and standard deviation (SD) of the BOLD response, PCr resynthesis rate and

MNSI score before (baseline) and after (follow-up) a control or exercise intervention observed in

the majority of longitudinal imaging studies. With data from 40 subjects included in the analysis according to the

		Ex	er
	Baseline		
Outcome	Mean	SD	T
BOLD respone	3.24	1.04	14
PCr resynthesis	41.16	14.1	~
MNSI	5.2	1.4	- Ta

ITT principal the study will have 80% power to detect a mean within-subject change in each outcome among subjects in each intervention group provided the change is between 10% and 18% when expressed as a percentage of the mean at baseline. The mean percentage change observed in the preliminary data among subjects

preliminary data.

 xercise
 Control

 Follow-up
 Baseline
 Follow-up

 Table 4. Expected mean and standard deviation (SD) of the within-subject change in BOLD response, PCr resynthesis rate, and MNSI score from baseline to after a control or exercise intervention based on the preliminary data in Table 3 and the conservative assumption of moderate within-subject correlation (p=0.5) between baseline and follow-up measures.

	Exer	cise	Control		
Outcome	Mean	SD	Mean	SD	
BOLD respone	1.11	1.26	0.18	1.42	
PCr resynthesis	10.61	12.85	0.06	8.53	
MNSI	1.20	1.78	NÁ		

CONFIDENTIAL

This material is the property of the NYU School of Medicine and Langone Medical Center. Do not disclose or use except as authorized in writing by the study sponsor

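### Baseline MNSI is tested as a predictor of change in MNSI itself, a pairing in which zero correlation is the wrong null

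*Combined protocol and SAP*

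**What the plan says.** Section 9.3.6 gives the exploratory objective as to "identify baseline factors (e.g., age, MNSI, general activity) predictive of improvement, represented as the baseline to follow-up change in each outcome". It adds that this "will be addressed using linear regression and bivariate correlations", stratified by intervention and then with both phases combined, weighted by compliance. Sections 2.3, 3.2.2 and 9.3 state the same objective.

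Section 9.3.2 brings the same factors into a model for the change in each outcome: "A second regression will be conducted with baseline factors (e.g., age, MNSI, general activity) added to the model".

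MNSI is also an outcome. It is in the Aim 1 list in 2.1 and 9.1, and Hypothesis 1c in 9.2 reads "Exercise will improve DPN symptoms, assessed with the MNSI".

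No section mentions regression to the mean, keeps an outcome's own baseline out of the predictor list, or names a null other than zero association.

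**The concern.** Change is follow-up minus baseline. When the predictor is that same baseline, measurement error and short-term fluctuation sit on both sides with opposite signs. A participant who scores high by chance at baseline tends to score lower later and is counted as improved. Baseline and change are then negatively correlated whether or not exercise works, and whether or not it works better in some people.

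The exploratory objective asks which patients benefit. The artefact would read as worse neuropathy at entry going with greater improvement, which is clinically plausible and so easy to accept. Exploratory status excuses low power and multiplicity. It does not help with a test whose expected result is non-zero when nothing differs between patients.

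**Working it through.** **Inputs, all from 9.4.** Alpha: "tests conducted at the two-sided 5% significance level". Sample size: the power statement opens "With data from 40 subjects included in the analysis according to the" ITT principle. Correlation: 0.5, described as a "conservative assumption of a moderate within-subject correlation". Baseline MNSI: mean 5.2, SD 1.4 (Table 3). MNSI change with exercise, mean and SD (Table 4): "MNSI 1.20 1.78".

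**Reproducing the plan's figures.** The preliminary changes as a percentage of the baseline mean are 1.11/3.24 = 34.3% (BOLD), 10.61/41.16 = 25.8% (PCr) and 1.20/5.2 = 23.1% (MNSI), matching the stated 23% to 34%. For MNSI, the change detectable with 80% power is (1.960 + 0.842) × 1.78/√40 = 0.79, or 15.2% of 5.2 (15.5% with the t distribution), inside the stated 10% to 18%. The inputs are therefore being read as the plan intends.

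**Expected correlation of baseline with change.** For baseline SD s1, follow-up SD s2 and correlation ρ,

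r = (ρ·s2 − s1) / SD(change), with SD(change)² = s1² + s2² − 2ρ·s1·s2.

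With no effect, or the same effect in everyone, s1 = s2 and this becomes r = −√((1 − ρ)/2). At ρ = 0.5, r = −0.50.

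**How often the test rejects.** By Fisher's z at ρ = 0.5: atanh(0.50) × √37 = 3.34, and Φ(3.34 − 1.96) ≈ 0.92. Simulation used normal scores, equal compliance weights, n = 40, equal SDs and at least 40,000 trials per setting:

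| ρ | expected r | rejection, baseline against change |
|---|---|---|
| 0.5 | −0.50 | 92% |
| 0.6 | −0.45 | 84% |
| 0.7 | −0.39 | 71% |
| 0.8 | −0.32 | 52% |
| 0.9 | −0.22 | 29% |

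Rounding scores to integers at ρ = 0.5 gives 94%. With 30 analysed participants the rates are 83%, 58% and 22% at ρ = 0.5, 0.7 and 0.9. A predictor unrelated to the outcome gives 5%.

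**The Table 4 figures taken literally.** Setting SD(change) = 1.78, s1 = 1.4 and ρ = 0.5 gives s2² − 1.4·s2 + 1.96 − 3.168 = 0, so s2 ≈ 2.00. Then r = (0.5 × 2.00 − 1.4)/1.78 ≈ −0.22, and the test rejects in about 29% of trials. A rise in SD from 1.4 to 2.0 does not fit a uniform effect, so this is a sensitivity case rather than a pure false-positive rate.

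**Oldham's method (change against the mean of baseline and follow-up).** With equal SDs it rejects in 4.8% to 5.1% of trials for ρ from 0.5 to 0.9. With SDs 1.4 and 2.00 and ρ = 0.5, r = (s2² − s1²)/(SD of change × SD of sum) = (4.01 − 1.96)/(1.78 × 2.96) ≈ +0.39. The simulated mean is about +0.38, with rejection in about 72% of trials. The sign reverses and rejection is more frequent than under the written method.

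**A control-phase comparator.** Attachment A schedules MNSI at weeks 0, 1 and 18 only, and Table 4 gives no control value for it. No MNSI is taken at the end of the control phase, so stratifying by intervention cannot show the slope expected without exercise.

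**The case against.** **The pairing is inferred.** It follows from MNSI being an example predictor and from the analysis covering each outcome; no sentence writes it out. Section 3.2.1 lists two MNSI scores (symptom questionnaire and physical exam), and Attachment A has MNSI at weeks 0 and 1. If the week 0 score were the predictor and change were taken from week 1 with the same instrument, a classical error model gives about 5% rejection. That is fair, but the plan says neither which score nor which visit is used, and the plain reading includes the coupled pairing.

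**The 92% is the top of a range.** The plan calls 0.5 conservative, says most longitudinal imaging studies show higher values, and gives no MNSI-specific correlation. The 5% level comes from the power section; 9.3.6 sets no threshold of its own. This stands, and the range should be quoted rather than the maximum.

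**Baseline does predict observed change, and adjusting for it is legitimate.** Both are true. The ANCOVA in 9.3 uses baseline MNSI as a covariate without error. The fault lies in testing or reading its coefficient as a sign of who benefits.

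**Wider inferences.** A reader might infer that the whole exploratory analysis, or the primary result, is compromised. The documents do not support this: age is not part of any change score, MNSI is not part of the imaging or ROS change scores, and the tests of mean change do not use this coefficient. A reader might also extend the point to general activity. Physical activity appears in 3.2.1 but not among the outcomes in 9.1 or the hypotheses in 9.2, so that extension is not established.

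**Conclusion.** The concern holds for one pairing: baseline MNSI as a predictor of MNSI change, in 9.3.6 and in the second regression of 9.3.2. There, a test against zero rejects in about 29% to 92% of trials at n = 40 when the effect is nil or uniform, depending on a correlation between 0.9 and 0.5; the Table 4 SDs also give about 29%.

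These figures assume normal scores, equal compliance weights, 40 analysed participants and a single-predictor test at the two-sided 5% level. The added covariates in 9.3.2 would alter the size, which was not calculated, but including them does not by itself remove the coupling. The consequence is confined to an exploratory claim about who improves. It is still worth correcting, because the written method would often produce that claim with no difference between patients behind it.

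**What to change.** In 9.3.2 and 9.3.6, state that an outcome's own baseline will not be tested or interpreted as a predictor of its own change. It may remain in the model as an adjustment covariate, and baseline MNSI may remain a predictor of the other outcomes. Naming the MNSI score and visit that serve as baseline would remove the ambiguity noted above.

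Do not name Oldham's method as a replacement without stating that it holds its 5% level only when baseline and follow-up variances are equal, which the Table 4 SDs contradict. Comparing baseline slopes between the exercise and control phases is possible only for outcomes measured at the end of the control phase, which excludes MNSI under the current schedule.

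The cost is a sentence or two of wording. No new data, visits or participants are needed. What is given up is a claim about differential benefit by baseline MNSI on the MNSI outcome, which the scheduled data could not support.

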## 9.4 Sample Size

Assessment of statistical power was based on tests conducted at the two-sided 5% significance level and the preliminary data in Table 3. Under the conservative assumption of a moderate within-subject correlation ( $\rho$ =0.5) between baseline and follow-up measures, the expected mean and SD of the within-subject change in the outcomes is given in Table 4. It is noted that statistical power will be higher if  $\rho$ >0.5 as observed in

Table 3. The mean and standard deviation (SD) of the BOLD response, PCr resynthesis rate and

MNSI score before (baseline) and after (follow-up) a control or exercise intervention observed in

the majority of longitudinal imaging studies. With data from 40 subjects included in the analysis according to the

		Ex	er
	Baseline		
Outcome	Mean	SD	T
BOLD respone	3.24	1.04	14
PCr resynthesis	41.16	14.1	~
MNSI	5.2	1.4	- Ta

ITT principal the study will have 80% power to detect a mean within-subject change in each outcome among subjects in each intervention group provided the change is between 10% and 18% when expressed as a percentage of the mean at baseline. The mean percentage change observed in the preliminary data among subjects

preliminary data.

 xercise
 Control

 Follow-up
 Baseline
 Follow-up

 Table 4. Expected mean and standard deviation (SD) of the within-subject change in BOLD response, PCr resynthesis rate, and MNSI score from baseline to after a control or exercise intervention based on the preliminary data in Table 3 and the conservative assumption of moderate within-subject correlation (p=0.5) between baseline and follow-up measures.

	Exer	cise	Control		
Outcome	Mean	SD	Mean	SD	
BOLD respone	1.11	1.26	0.18	1.42	
PCr resynthesis	10.61	12.85	0.06	8.53	
MNSI	1.20	1.78	NÁ		

CONFIDENTIAL

This material is the property of the NYU School of Medicine and Langone Medical Center. Do not disclose or use except as authorized in writing by the study sponsor

in the exercise group ranged from 23% to 34% across outcomes, implying that the study will have >80% power to detect anticipated changes resulting from exercise. The minimum difference in terms of the mean within-subject change in a given outcome that is detectable with 80% power is 4.5% for BOLD response and 120% for PCr resynthesis where each difference is expressed as a percentage of the mean within-subject change. The difference in terms of the mean within subject change observed in the preliminary data was 5.2% for BOLD response and 176% for PCr resynthesis, respectively. Since the observed differences exceed the minimum detectable differences, the study will have >80% power to detect anticipated group differences.

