# 9 Statistical Considerations

# 9.1 Statistical and Analytical Plans

The primary objective is to assess and compare the interventions (exercise versus control phase in the same individual) in terms of the baseline to follow-up change in the following outcomes: 1) DTI, plasma ROS level, and the MNSI assessment of DPN symptoms (Aim 1); and 2) leg mitochondrial function, oxidative capacity (31P-MRI), peak MV response (BOLD-MRI), the proportion of fat-free muscle (IDEAL-MRI) and leg muscle strength (Aim 2).

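### Section 9.4 prints multiples of the control-phase change as percentages, and its >80% power for the BOLD phase comparison is not established because no correlation between the two phase changes is stated

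*Combined protocol and SAP*

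**What the plan says.** Sections 2.1 and 9.1 make the primary objective a comparison of changes, described in 9.1 as "exercise versus control phase in the same individual". Section 9.4 supports it in two steps.

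- **Pre-post change.** With 40 participants there is 80% power to detect "a mean within-subject change in each outcome among subjects in each intervention group", if the change is 10% to 18% of the baseline mean. This rests on "the conservative assumption of a moderate within-subject correlation", 0.5, between baseline and follow-up. The section adds: "It is noted that statistical power will be higher if" that correlation exceeds 0.5.
- **Exercise versus control.** The minimum difference "detectable with 80% power is 4.5% for BOLD response and 120% for PCr resynthesis where each difference is expressed as a percentage"; the base is the average change within participants. The preliminary difference "was 5.2% for BOLD response and 176% for PCr resynthesis, respectively". Because the second pair exceeds the first, "the study will have >80% power to detect anticipated group differences".

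Section 9.3.5, by contrast, says: "Therefore, there will be no comparison between groups".

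On imaging, Sections 1.2 and 3.1 describe MRI at baseline, before exercise and after exercise, and Attachment A places it at weeks 1, 5 and 18. Section 9.3.1 counts two imaging occasions (visits 1 and 3), and Section 12.3 pays for two scans.

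**The concern.** Three things in this part of the plan do not fit together.

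First, a detectable difference of 4.5% for one outcome and 120% for another, both described as percentages of a mean change, cannot be matched to Table 4 as labelled.

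Second, the difference between two changes in one person has a variance that depends on the correlation between those changes. With three scans, the pre-exercise scan ends the control phase and starts the exercise phase, so it enters the two changes with opposite sign. Section 9.4 gives a correlation between baseline and follow-up but none between the phase changes, and it writes of groups although there is one cohort.

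Third, with only two scans no control-phase MRI change exists, and the primary MRI comparison cannot be made.

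At stake is the power justification for the primary comparison on BOLD (Hypothesis 2b), and whether the MRI comparison can be carried out at all.

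**Working it through.** **Inputs.** From Section 9.4: n = 40, two-sided 5%. From Table 4, mean (SD) of the within-subject change, at a baseline to follow-up correlation (rho) of 0.5:

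- BOLD: exercise 1.11 (1.26), control 0.18 (1.42)
- PCr: exercise 10.61 (12.85), control 0.06 (8.53)

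The correlation r between the two phase changes is not stated, so it is varied below.

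**1. Reproducing the printed figures.**

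- BOLD: 1.11 - 0.18 = 0.93, and 0.93 / 0.18 = 5.17, printed as 5.2%. As a percentage it is about 517%.
- PCr: 10.61 - 0.06 = 10.55, and 10.55 / 0.06 = 175.8, printed as 176%. As a percentage it is about 17,580%.

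The detectable figures are on the same scale: 4.5 × 0.18 = 0.81 and 120 × 0.06 = 7.2 in outcome units. Both sides of the plan's comparison carry the same factor of 100, so their order does not change.

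**2. Power for the phase comparison.** The check uses an unweighted paired t-test on (exercise change - control change), with noncentral t:

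SD of contrast = sqrt(s1² + s0² - 2·r·s1·s0)

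For n = 40, 80% power needs difference / SD = 0.4543. The contrast SD may therefore be at most 0.93 / 0.4543 = 2.05 for BOLD and 10.55 / 0.4543 = 23.2 for PCr.

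| r | BOLD SD | BOLD detectable | BOLD power | PCr SD | PCr detectable | PCr power |
|---|---|---|---|---|---|---|
| +0.27 | 1.62 | 0.74 | 94% | 13.37 | 6.07 | >99% |
| 0 | 1.90 | 0.86 | 86% | 15.42 | 7.01 | 99% |
| -0.25 | 2.12 | 0.96 | 77% | 17.11 | 7.77 | 97% |
| -0.5 | 2.32 | 1.05 | 69.5% | 18.64 | 8.47 | 94% |

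BOLD power crosses 80% at r of about -0.16. PCr power stays above 80% at every r; it is 86% even at r = -1.

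**3. Which values of r are plausible.** Suppose the three scans have equal variances, adjacent scans have correlation rho, and scans 1 and 3 have correlation c. Then

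r = (2·rho - 1 - c) / (2·(1 - rho))

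At rho = 0.5 this reduces to r = -c. So c = 0.5 (one correlation for all pairs) gives r = -0.5; c = 0.25 (correlation decaying as 0.5²) gives r = -0.25; c = 0 gives r = 0. With unequal variances r can be positive: at rho = 0.5 and c = 0, the covariance of the changes is SD2 × [(SD1 + SD3)/2 - SD2], which is above zero when the middle scan is less variable than the average of the other two. The documents do not fix c or the scan variances.

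**4. Effect of a higher rho.** If c equals rho, r stays at -0.5 and the change SDs scale by sqrt((1 - rho)/0.5). The BOLD contrast SD is then 2.08 at rho = 0.60 (power 79%), 2.02 at 0.62 (81%) and 1.80 at 0.70 (89%). Power reaches 80% at rho of about 0.61.

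**5. Pre-post claim.** For BOLD, 0.4543 × 1.26 / 3.24 = 17.7% of baseline, within the plan's 10% to 18% and well below the expected 1.11 / 3.24 = 34%.

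**6. Scan count.** Three scans (1.2, 3.1, Attachment A) give both a control-phase and an exercise-phase change. Two scans at visits 1 and 3 (9.3.1, and the count in 12.3) give one overall change and no control-phase change.

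**The case against.** The plan calls rho = 0.5 conservative and says that power rises above it. That stands: even at r = -0.5, a rho of about 0.61 restores 80%. A BOLD shortfall therefore needs both the plan's cautious rho and a sufficiently negative r. Positive values of r are also possible and give higher power.

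A reader might infer that the plan overlooked the shared scan and treated the phases as independent. The documents do not support this as fact. The printed ratios do not reproduce under independence. For BOLD, 4.5/5.2 × 0.93 = 0.80, against 0.86 at r = 0; with the Table 4 SDs that corresponds to r of about +0.13. For PCr, 120/176 × 10.55 = 7.19, which corresponds to about -0.06. Only the absence of a stated correlation can be asserted.

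A reader might also try to test Table 4 by putting the exercise-baseline SDs of Table 3 into the control phase. The control columns of Table 3 are not legible in the text available here, so that substitution proves nothing about the control SDs.

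Finally, the unweighted paired test is simpler than the weighted ANCOVA of Section 9.3, and the tests in Section 9.3.2 are baseline-versus-follow-up, for which the pre-post power claim holds. Both points are fair. Compliance weights and covariates are not modelled here, so the figures are approximate.

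**Conclusion.** The percentage labels are wrong by a factor of 100. This rests on Table 4 alone and does not itself alter the power conclusion.

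The unqualified >80% for the BOLD phase comparison is not established. On the Table 4 SDs, power runs from about 94% to 69.5% over r from +0.27 to -0.5, and reasonable correlation structures fall on both sides of 80%. A reader might conclude that the trial is underpowered for BOLD or needs more participants. The documents do not support that, because they give no value of r and power improves if rho exceeds 0.5. For PCr, >80% holds on the Table 4 SDs.

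The scan counts contradict each other. If two were correct, the primary MRI comparison in Sections 2.1 and 9.1 could not be made. This should be fixed before analysis.

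**What to change.** (a) In Section 9.4, give the expected and detectable differences in outcome units: expected 0.93 (BOLD) and 10.55 (PCr). Drop the ratios to the control change, which for PCr divide by a value near zero.

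(b) State that the comparison is the within-person difference between the exercise-phase and control-phase changes, and give the assumed correlation between them. Make the BOLD power conditional on it: 80% needs a contrast SD of at most 2.05. With the Table 4 SDs, detectable differences run from 0.74 to 1.05 and power from about 94% to 69.5% for correlations from +0.27 to -0.5, with higher power if rho exceeds 0.5. Keep >80% for PCr, stated as resting on the Table 4 SDs. Write phase in place of group.

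(c) Reconcile the scan count in Sections 9.3.1 and 12.3 with Sections 1.2 and 3.1 and Attachment A.

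The cost is rewording in Section 9.4 and a consistency edit in two other sections. No participants or visits are added if three scans are intended.
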